Myocardial Infarction	TIA										
Secondary Endpoints	
Safety
 
 
Incidence of Serious Adverse Device Effects (SADEs)
 
Incidence of Serious Adverse Events (SAEs) within 7 days (early-onset), >7-30 days (peri-procedural) and >30 days (late onset) of initial ablation procedure
 
Incidence of non-serious adverse events
 
Incidence of pre-and post-ablation asymptomatic and symptomatic cerebral emboli as determined by MRI evaluations
 
Incidence of new or worsening neurological deficits compared to baseline
 
Summary of NIHSS, mRS and MoCA scores at baseline and follow-up timepoints
 
 
Effectiveness
 
 
PVI achieved with TGA mode only among all targeted veins and by subject
 
PVI achieved with combined use of TGA and Q-mode among all targeted veins and by subject
 
Ablation of acute reconnection (touch-up) among all targeted veins and by subject
 
Ablation by a non-study catheter among all targeted veins and by subject
 
Touch-up applications with TGA, Q-mode and non-study catheter applications
 
 
Additional analyses on procedural data, including but not limited to:
 
 
Use of QDOT Micro™ catheter ablation outside the PV area
 
Use of a non-study catheter for ablation outside the PV area
 
Total procedure time, mapping time, PV ablation time, total ablation time, RF application time, LA dwell time
 
Total number of RF applications, % TGA applications and % Q-mode applications
 
Anatomical location of touch-up applications
 
Temperature, power, contact force, impedance
 
										

	
 
- Total Fluoroscopy time/dose
 

Inclusion Criteria	
Subjects must meet ALL the following inclusion criteria to be eligible for participation in this clinical investigation:
 
 
1. Age 18 or older.
 
2. Signed the Patient Informed Consent Form (ICF).
 
3. Diagnosed with symptomatic PAF
 
4. Selected for catheter ablation through pulmonary vein isolation.
 
5. Able and willing to comply with all pre-, post-, and follow-up testing and requirements (e.g. patient not confined by a court ruling).
 

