## **8.3. Post-Ablation Follow-up Schedule**

The subject will be required to complete follow up visits through 3 months post initial ablation procedure. Follow-up will be done at 7 days (phone call or clinic visit), 1 month (if applicable) and 3 months (clinic visits).

Discharged subjects will receive a telephone call or have a clinic visit at 7 days (7D, day 6-8) post ablation procedure to assess cardiac medication AFL/AF/AT occurrences and occurrence of (Primary) Adverse Events.

The subject will be required to complete follow up through 3 months post initial ablation procedure. The follow-up visits are 1 month  $\pm$  7 days (1M, day 23-37) (if applicable) and 3 months  $\pm$  14 days (3M, day 76-104) post ablation procedure. Follow-up visit schedule should be based on the date of the index study ablation procedure and will not reset if subject undergoes a repeat AF ablation procedure.

- If findings of micro-emboli/neurologic deficits/ CVA or TIA events identified at a prior evaluation (i.e. pre-discharge) a 1 month follow up visit will be performed with the following assessment:
  - Cerebral MRI, Neurological Exam and NIH Stroke Scale (NIHSS), MoCA and mRS assessments. Subjects with findings of micro-emboli/neurologic deficits/CVA/TIA will undergo additional MoCA/mRS through 3M follow-up
- At the 3 months post ablation procedure visit (clinic visits) the following assessments should be performed:
  - Cardiac medication and anticoagulation regimen (only cardiac related AADs, anticoagulation regimen, etc.)
  - Medical / Hospitalization History
  - NYHA Functional Class Scale.
  - ECG in case of standard of care
  - Adverse events, if any
  - AFL/AT/AF occurrence and repeat ablation
  - Cerebral MRI, Neurological Exam and NIH Stroke Scale (NIHSS) and MoCA/mRS assessments will be performed in case observations findings of micro-emboli/neurologic deficits were noted during previous assessments. A certified/qualified physician must perform neurologic exams at pre-and post-ablation and possibly at other follow-up visits, pending findings of micro-emboli/neurological deficits.
  - End of Study Follow up

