### 9.1.3. Primary Adverse Event (PAE)

A Primary AEs is an event listed in Table 4 which occurs within the first week (7 days) following an ablation procedure. Primary AEs are considered SAEs.

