### **9.3. Time Period and Frequency for Event Assessment and Follow-up**

The investigator, or designated individual, will record all reportable events with start dates occurring any time after informed consent is obtained. At each study visit, the investigator will inquire about the occurrence of AE/SAEs since the last visit.

All AE/SAEs need to be followed until the event is resolved (with or without sequelae). The medical monitor or designee of this clinical investigation will decide if more follow up information is needed in case the event is not resolved at study completion. All required treatments and outcomes of the SAE must be recorded in the eCRF.

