5.2 Secondary Endpoints

- **Safety**
 - Incidence of Serious Adverse Device Effects (SADEs)
 - Incidence of Serious Adverse Events (SAEs) within 7 days (early-onset), >7-30 days (peri-procedural) and >30 days (late onset) of initial ablation procedure
 - Incidence of non-serious adverse events
 - Incidence of pre-and post-ablation asymptomatic and symptomatic cerebral emboli as determined by MRI evaluations
 - Incidence of new or worsening neurological deficits compared to baseline
 - Summary of NIHSS, mRS and MoCA scores at baseline and follow-up timepoints
- **Effectiveness**
 - PVI achieved with TGA mode only among all targeted veins and by subject
 - PVI achieved with combined use of TGA and Q-mode among all targeted veins and by subject
 - Ablation of acute reconnection (touch-up) among all targeted veins and by subject
 - Ablation by a non-study catheter among all targeted veins and by subject
 - Touch-up applications with TGA, Q-mode and non-study catheter applications
- **Additional analyses on procedural data, including but not limited to:**
 - Use of QDOT Micro™ catheter ablation outside the PV area
 - Use of a non-study catheter for ablation outside the PV area

- Total procedure time, mapping time, PV ablation time, total ablation time, RF application time, LA dwell time
- Total number of RF applications, % TGA applications and % Q-mode applications
- Anatomical location of touch-up applications
- Temperature, power, contact force, impedance
- Total Fluoroscopy time/dose

6 Levels of Significance

All data will be summarized by descriptive analyses. No formal statistical inference will be made. Sub-analyses will be done for subjects where TGA was the only application mode used and for subjects where applications were done through a combination of TGA and Q-mode. Where confidence intervals are used they will be two-sided 95% confidence intervals, unless stated otherwise.

7 Analysis Sets

The following analysis populations will be used to complete the analyses of data:

- **Safety Population (SP):** The safety population will include all enrolled subjects who have the investigational device inserted, regardless if RF energy is delivered. All safety analyses will be performed on the Safety Population.

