10.4 Primary and Secondary Endpoint Analyses

Primary Safety

Primary safety outcome will be reported as primary adverse events (PAEs) (within 7 days of the intial mapping and ablation procedure, with exception for PV stenosis, death, tamponade and AEF). The number of events and the number and percentage of subjects experiencing primary adverse events will be reported. The primary safety endpoint will be summarized overall and by AE type, seriousness, severity, causality, anticipated or not. The Primary Safety analysis will be performed on the Safety Population.

Primary Effectiveness

Acute Procedural Success: Acute success is defined as achieving confirmation of entrance block in all targeted PVs after adenosine and/ or isoproterenol challenge. The number and percentage of subjects who have reached acute success will be summarized. Primary Effectiveness analysis will be performed on the Effectiveness Population.

Secondary Safety

The number of events and the number and percentage of subjects with SADEs, SAEs and non-SAEs during follow-up period (3 months) will be summarized overall and by AE type, seriousness, severity, causality, timing (< 7 days, 7-30 days, > 30 days), and outcome etc. The subjects with SADEs and SAEs will also be listed.

The number of events and the number and percentage of subjects with pre- and post-ablation asymptomatic and symptomatic cerebral emboli as determined by MRI evalutaions will be summarized. The incidence of new or worsening neurological deficits compared to baseline will be summarized and listed. NIHSS, mRS and MoCA scores at baseline and follow-up timepoints will be summarized and listed as well. The NAE endpoints will be analyzed in the NAE population.

Secondary Effectiveness

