Appendix: Tables, Listings and Graphs Shells

The tables, listings and graphs shells will be approved and provided separately.

End of Document

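### The SAE timing rows in SAP 10.4 contradict the endpoint's own windows on day 7, so a day-7 SAE would be tabulated outside the early-onset row if the text is followed as written

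*SAP*

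**What the plan says.** **The endpoint.** SAP 5.2 lists SAE incidence "within 7 days (early-onset), >7-30 days (peri-procedural) and >30 days (late onset) of initial ablation procedure". Protocol 3.2.2 and 14.4.2 use the same three windows, as does the Protocol Summary, which begins "Incidence of Serious Adverse Events (SAEs) within 7 days (early-onset".

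**The tabulation rule.** SAP 10.4, Secondary Safety, says that SADEs, SAEs and non-serious events over the 3-month follow-up will be broken down by several attributes, including "timing (< 7 days, 7-30 days, > 30 days". It also says that subjects with SADEs or SAEs will be listed.

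**Related text.**
- The Primary Safety paragraph of the same SAP section sets the general PAE window as "within 7 days of the intial mapping and ablation procedure".
- Protocol 9.1.3: "Primary AEs are considered SAEs".
- Protocol 9.3 works from event dates: the investigator "will record all reportable events with start dates occurring any time after informed consent is obtained".
- Protocol 8.3 sets the first follow-up contact: "Discharged subjects will receive a telephone call or have a clinic visit at 7 days (7D, day 6-8) post ablation procedure".
- SAP Appendix: "The tables, listings and graphs shells will be approved and provided separately".

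**The concern.** For this secondary endpoint the time windows are the definition, and SAP 10.4 is the only place that says how the events will be split into those windows. Its rows are not the endpoint's rows. The first stops before day 7 and the second starts on day 7, whereas the endpoint keeps day 7 in the early-onset window.

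Two things are at stake. The first row of the table would cover a shorter window than the early-onset endpoint it is meant to report. And two tables specified in the same SAP section would place one event differently: a PAE starting on day 7 would fall inside the 7-day primary window but in the 7-30 day SAE row.

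**Working it through.** The documents give no power, alpha or sample-size calculation that bears on this point, so there is no stated figure to reproduce. The check is to classify each onset day under both rules.

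**Inputs**
- Endpoint rule (SAP 5.2; Protocol Summary, 3.2.2, 14.4.2): early if d ≤ 7; middle if 7 < d ≤ 30; late if d > 30.
- Tabulation rule (SAP 10.4): first row if d < 7; second if 7 ≤ d ≤ 30; third if d > 30.
- d = onset date minus procedure date, in whole days. Protocol 9.3 refers to start dates, so day 7 is a full calendar day.
- Days 0 to 104 were checked, 104 being the end of the 3-month visit window.
- N = 50 in the Safety Population (assumption, from the planned sample size).

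**Step 1: compare the rules**

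| Onset day | Endpoint rule | SAP 10.4 rule | Agree? |
|---|---|---|---|
| 0-6 | early | first row | yes |
| 7 | early | second row (7-30) | **no** |
| 8-30 | middle | second row | yes |
| 31-104 | late | third row | yes |

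Day 7 is the only day classified differently. Day 30 falls in the middle under both rules.

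**Step 2: could a lost symbol explain it?** Suppose the first SAP 10.4 row was meant as ≤7 and the sign was lost when the PDF was read. The second row still begins at 7, so day 7 would satisfy both d ≤ 7 and 7 ≤ d ≤ 30 and fall in two rows. The line needs correcting on either reading.

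**Step 3: which calendar day is day 7?** The midpoints of the visit windows in Protocol 8.3 are (6 + 8)/2 = 7 for 7 days, (23 + 37)/2 = 30 for 1 month and (76 + 104)/2 = 90 for 3 months. The 7-day contact is centred on day 7 after the procedure, which makes the procedure date day 0. Had the procedure date been day 1, seven days later would be day 8.

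**Step 4: size for one subject.** 1/50 = 2.0 percentage points.
- Only SAE on day 7: early row −2.0, 7-30 row +2.0.
- Another SAE before day 7: early row unchanged, 7-30 row +2.0.
- Another SAE on days 8-30: early row −2.0, 7-30 row unchanged.

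In the event-count rows, one event moves each time. The total SAE count does not change. The primary PAE count does not change either, because it uses its own window.

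**Step 5: after correction.** With rows ≤7, >7-30 and >30, no day from 0 to 104 is classified differently.

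**The case against.** The case for leaving this alone is that it is editorial. The endpoint is stated consistently in all four places that define it, and only a parenthesis in an open-ended list of breakdowns differs. SAP 10.4 does not label its first row early-onset. The study is descriptive, and the subject listings would let a reader re-bin a day-7 event if they show onset dates. All of this stands, and it limits the severity. It does not reconcile the text: the SAP gives two rules for one endpoint.

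Some stronger readings are tempting but not supported:

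- **A day-7 SAE will be misreported.** The table shells are separate documents, and SAP 5.2 carries the endpoint's own windows, so the programmed tables may be right. The claim must stay conditional on SAP 10.4 being followed as written.
- **The primary safety result is affected.** It is not, because the PAE window in SAP 10.4 includes day 7.
- **The primary table and the early-onset SAE row should otherwise match.** They need not. Some PAE types count after day 7 (SAP 5.1 and 10.4), and not every SAE is a PAE.
- **Day numbering is wholly open.** No explicit rule for event onset is given, but the visit windows imply that the procedure date is day 0. The numbering neither creates nor removes the mismatch.
- **A day-7 onset will be dated by recall at month 3 if the 7-day contact falls on day 6.** Protocol 9.3 already has the investigator ask at each visit about events since the last one, and Protocol 9.4 requires SAEs to reach the sponsor within 72 hours of awareness. The documents do not show that recall would be the usual source of an SAE date.

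**Conclusion.** Wrong as written, low severity. SAP 10.4 contradicts SAP 5.2 and the protocol on one onset day. If it is followed literally, a day-7 SAE moves from early-onset to the 7-30 day row, and a day-7 PAE is placed differently in the primary and secondary safety tables.

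The size is one boundary day and at most 2.0 percentage points per subject in a row, assuming 50 subjects in the Safety Population and each subject counted once per row. The documents give no basis for estimating how many SAEs would start on day 7, so no expected shift can be given. The conclusion rests on timing being derived from whole calendar dates. The contradiction itself concerns SAEs, since the endpoint lists give no time windows for the separate SADE and non-serious event endpoints.

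**What to change.** In SAP 10.4, Secondary Safety, replace the timing rows with ≤7, >7-30 and >30 days after the initial ablation procedure, classified by recorded onset date. Add one sentence stating that the procedure date is day 0, in line with the visit windows in Protocol 8.3. Use the same row headings in the separate table shells.

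The cost is one corrected line, one added sentence and a check of the shell headings. Data collection and study conduct are unaffected, and the change only restores the sponsor's own endpoint definition.

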- **Cerebral MRI, Neurological Exam and Neurological Evaluation** using the Montreal Cognitive Assessment (MoCA), NIH Stroke Scale (NIHSS) and Modified Rankin Scale (mRS) are required to be performed within 72- hours pre-procedure to evaluate the neurological condition and presence of neurological deficits of the subjects before undergoing study ablation procedure. A certified/qualified physician expert must perform neurologic exams at pre- and post-ablation and possibly at other follow-up visits, pending previous findings of micro-emboli/neurologic deficits.

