#### **8.2.4. Pre-Discharge Assessments**

Prior to hospital discharge, the following assessments should be performed:

- **Cardiac medication and anticoagulation regimen** (only cardiac related AADs, anticoagulation regimen, etc.)
- **ECG** in case of standard of care
- **Endoscopy:** imaging of the esophagus for the detection of esophageal injury within 72 hours post-procedure; prior to discharge.
- **Transthoracic echocardiogram (TTE)** to assess the pericardium. In the event of a significant pericardial effusion is identified, subjects should be followed until the condition resolves.
- **Adverse events**, if any
- **Occurrence of AF or other arrhythmias**, if any
- **Cerebral MRI** (within 72hours post procedure), Neurological exam and Neurological Evaluation using the NIH stroke Scale (NIHSS) within 72- hours post procedure, prior to discharge. A certified/qualified physician expert must perform neurological exams.

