**Table 3 Summary of Subject Assessments**

Assessments	Pre-ablation	Pre-discharge	7D (D6-8)	M1 (D23-37)	M3 (D76-104)	UNS
Clinic visit	●			● 9/10	●	●
Phone Call			● 			
Patient Informed Consent  /Demographics	●					
Medical/AF history	●					
Cardiac Medication and anti-coagulation Regimen	●	●	●	● 	●	●
CHA2DS2-Vasc Score	●					
NYHA functional Class Scale	●				●	
Pregnancy Test	● 					
Transthoracic Echo (TTE)	● 	●				
LA thrombus detection	● 					
ECG	● 	● 			● 	● 
Adverse events	●	●	●		●	●
AFL/AT/AF occurrence and repeat ablation		●	●		●	●
Endoscopy		● 				
Cerebral MRI	● 	● 		● 	● 	● 
Neurological Exam	● 	● 		● 	● 	● 
NIH Stroke Scale	● 	● 		● 	● 	● 
mRS	● 			● 	● 	● 
MoCA	● 			● 	● 	● 

1. May be substituted with a clinic visit.
2. To be completed within 60 days prior to ablation procedure
3. In all women of childbearing age and potential. To be completed within 1 week prior to ablation procedure.
4. To be performed within 30 days prior to procedure to determine the LA size and LVEF%, if the subject has undergone an imaging procedure within the last 6 months where the atrial size was assessed, the pre-procedure imaging assessment is not required.
5. To be completed the day before or the day of the study ablation procedure. Imaging modality TEE, ICE, CT or MRI.
6. To be collected if completed as standard of care.
7. To be completed within 72-hours pre-procedure.
8. To be completed within 72-hours post-procedure.
9. To be undertaken/collected if neurologic symptoms and/or new cerebral ischemic lesions identified/CVA/TIA reported in a prior evaluation.
10. To be completed only if a previous mandated test was missed, or if subject reports neurologic difficulties between scheduled follow-up visits and unscheduled assessment per investigator approval

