- **Effectiveness Population (EP):** The effectiveness population will include all enrolled subjects, have had the investigational device inserted and underwent ablation with the study catheter used in conjunction with TGA mode for PVI. The subjects without any TGA mode application for PVI will be excluded from the effectiveness population. All effectiveness analysis will be performed on the Effectiveness Population.
- **Neurological Assessment Evaluable (NAE) Population:** The NAE Population will include all enrolled subjects have been treated with the study catheter and have any post-ablation neurological assessment. Assessment of incidence of new lesions requires availability of pre-and post MRI. The subjects without pre-MRI but no lesion on post-MRI will be included in the NAE population. Assessment of incidence of new deficits requires availability of pre-and post-neurological evaluation. Analysis of neurological data will be performed on the NAE Population.

8 Sample Size Justification

This is a clinical feasibility study for evaluation of safety and acute performance of THERMOCOOL SMARTTOUCH® SF-5D system with TGA mode application for PVI. This clinical investigation is intended to provide preliminary estimates of safety and acute performance. Enrollment in the clinical investigation will be approximate 50 subjects,

distributed over up to 10 centers in Europe. Minimum attrition is expected for safety assessment. No more than 10% attrition is expected to assess effectiveness outcomes.

Because this study is a feasibility study, there is no statistical power calculation and no hypothesis to be tested. 50 subjects are deemed sufficient to clinically characterize safety and acute outcomes.

9 Data Monitoring Committee (DMC)

Safety review will be performed by the medical safety officer as described by Safety Management Plan.

10 Analyses to be Conducted

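### Follow-up MoCA and mRS scores, and one- and three-month NIHSS scores, come from subjects tested because of a finding, but the SAP sets them beside a near-whole-cohort baseline with no paired analysis

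*SAP*

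**What the plan says.** **Baseline.** Protocol 8.2.1 lists the cerebral MRI, the neurological exam, MoCA, NIHSS and mRS, which "are required to be performed within 72- hours pre-procedure to evaluate the neurological condition and presence of neurological deficits of the subjects". This applies to every subject.

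**Pre-discharge.** Protocol 8.2.4 requires "Neurological exam and Neurological Evaluation using the NIH stroke Scale (NIHSS) within 72- hours post procedure, prior to discharge". MoCA and mRS are not in that list, and their pre-discharge cells in Table 3 are empty.

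**One and three months (M1, M3).** The NIHSS, mRS and MoCA cells in Table 3 all carry footnote 9: "To be undertaken/collected if neurologic symptoms and/or new cerebral ischemic lesions identified/CVA/TIA reported in a prior evaluation". Protocol 8.3 repeats the restriction. At three months, for example, these assessments "will be performed in case observations findings of micro-emboli/neurologic deficits were noted during previous assessments".

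**Unscheduled visits.** Footnote 10 of Table 3 reads "To be completed only if a previous mandated test was missed, or if subject reports neurologic difficulties between scheduled follow-up visits".

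**Analysis.** SAP section 7 defines the population: "The NAE Population will include all enrolled subjects have been treated with the study catheter and have any post-ablation neurological assessment". Section 10.4 adds "The NAE endpoints will be analyzed in the NAE population" and, for the scores, only that "NIHSS, mRS and MoCA scores at baseline and follow-up timepoints will be summarized and listed as well". The conventions in SAP 10.1 are the number with data, mean, SD, median, minimum and maximum. SAP 10.6 rules out imputation.

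**The concern.** The score summary is a named secondary safety endpoint, and in a purely descriptive study the summaries are the whole result. A reader will naturally compare the baseline row with the one- and three-month rows to see whether cognition or function moved. Those rows describe different people. The first covers nearly everyone treated; the later ones cover subjects selected because something had been found.

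The comparison could suggest a decline, or hide one, simply because tested subjects started from a different level than untested ones. For MoCA and mRS there is no follow-up value taken in all subjects to fall back on.

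**Working it through.** The plan states no figure for this point, so there is none to reproduce. The check has two parts.

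**1. Who is tested at each scheduled visit** (Table 3, Protocol 8.2.1, 8.2.4 and 8.3)

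| Score | Baseline | Pre-discharge | M1 | M3 | Post-baseline visits covering everyone |
|---|---|---|---|---|---|
| MoCA | all | not scheduled | triggered | triggered | 0 of 2 |
| mRS | all | not scheduled | triggered | triggered | 0 of 2 |
| NIHSS | all | all | triggered | triggered | 1 of 3 |

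The trigger lists in footnote 9 and in Protocol 8.3 differ slightly (symptoms, for instance, appear only in the footnote). Both restrict testing to subjects in whom a preceding assessment showed a neurological or MRI abnormality. Unscheduled tests under footnote 10 are selective too.

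One post-ablation neurological assessment of any kind admits a treated subject to the NAE population. The pre-discharge examination, due in everyone, is enough. If the schedule is followed, the NAE population is therefore close to the whole treated cohort, and so is its baseline summary.

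**2. What the difference between the two summaries contains**

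Let N be the NAE subjects with a baseline score and n those who also have the follow-up score. Let B_T and B_U be the baseline means of tested and untested subjects, F_T the follow-up mean of the tested, and d = B_T − B_U.

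- Baseline mean of all: B_all = (n/N) B_T + (1 − n/N) B_U
- Hence B_T − B_all = (1 − n/N)(B_T − B_U) = (1 − n/N) d
- Hence F_T − B_all = (F_T − B_T) + (1 − n/N) d

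The first term is the mean within-subject change in tested subjects. The second is due only to the change of population.

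Inputs: N = 50 is the planned enrolment (Protocol 14.7), taken here as the NAE size. The documents do not give n, so a range is assumed.

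| n (assumed) | 1 − n/N | Population part |
|---|---|---|
| 5 | 1 − 5/50 = 0.9 | 0.9 d |
| 10 | 1 − 10/50 = 0.8 | 0.8 d |
| 20 | 1 − 20/50 = 0.6 | 0.6 d |

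The fewer subjects triggered, the more of any baseline gap passes into the comparison. The documents do not give d either. It may be zero and may have either sign. Purely as a scale, if d were half a standard deviation in either direction, the population part at n = 5 would be 0.9 × 0.5 = 0.45 SD in that direction, with no true change in anyone.

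If the baseline is restricted to the same n subjects, the second term is zero whatever n and d are.

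**The case against.** The strongest reply is that the SAP never plans the subtraction. It promises summaries and listings, without inference, in a feasibility study of about 50 subjects. Change from baseline has its own endpoint, the incidence of new or worsening deficits, for which SAP section 7 already requires pre and post evaluations. The number with data would show the drop, and with few triggered subjects the listings would let a reader pair values by hand. The table shells are provided separately and might contain change columns. Exclusion criterion 32 (unresolved pre-existing neurological deficit) may also narrow the baseline spread of NIHSS, and perhaps of mRS, which limits d for those scores.

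Much of this stands as a limit on importance. The deficit and lesion incidence endpoints are not affected, nor is baseline against pre-discharge NIHSS. The exclusion criterion makes MoCA the score most exposed, with mRS next.

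It does not remove the point. The deficit endpoint is binary and is not built on these scores. The counts and listings reveal the mismatch but do not separate change from composition. Unseen shells cannot supply a method that the SAP text does not state. The exclusion criterion does not constrain MoCA.

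**Conclusion.** The concern holds and is minor. Followed as written, the SAP sets a baseline from nearly all treated subjects beside one- and three-month MoCA, mRS and NIHSS scores from a finding-triggered subset, with no within-subject change or matched baseline. The population part of a difference in means is exactly (1 − n/N) × d: 0.9d, 0.8d or 0.6d for n = 5, 10 or 20 of 50. This rests on an NAE population of 50 with baseline scores, on assumed values of n, and on an unknown d, so no bias of any given size or direction is claimed. No primary endpoint, incidence estimate or decision rule is touched.

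**What to change.** In SAP section 10.4, for MoCA, mRS and the one- and three-month NIHSS:

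1. Report within-subject change in subjects with both values, using a baseline-to-follow-up shift table for mRS, beside the baseline summary of those same subjects.
2. Label these results as the subset tested because of the protocol trigger. Identify make-up and unscheduled tests separately. Show the number tested out of the number in the NAE population.
3. State that change in MoCA and mRS cannot be estimated in untested subjects. Pairing removes the population term but not the selection, so the results should not be read as change in the whole cohort.

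Leave the rules for new lesions and new deficits in SAP section 7 as they are. The cost is SAP and table-shell wording only, with no added data or visits.
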